Hamilton J, 1988 [Esophagitis]	3	3 days	15	No acid exposure time reduction nor clinical improvement	Low power Short follow-up	19
Pollmann H, 1996 [GERD]	NA	2 weeks	NA	No clinical improvement	Full text unavailable Non-structured abstract	21
Khan BA, 2012 [Nocturnal GERD]	1	1 week	20	↓ acid exposure time, clinical improvement	Non-randomized Inpatient setting	18

Table 1: Summary of HBE clinical trials in GERD published to date. NA: Unavailable; PPI: proton pump inhibitor; ↓: reduction

HYPOTHESIS

Head of bed elevation is a useful treatment for patients with GERD and nocturnal symptoms, and has a positive impact in quality of life in these patients.

STUDY OBJECTIVES

General Objective: To assess the effectiveness of HBE for treatment of patients with GERD and nocturnal symptoms, and to determine the impact of this intervention in quality of life of these patients.

Specific Objectives:

- 1. To identify, recruit and randomize participants with strict allocation concealment.
- 2. To compare symptom severity and quality of life among participants allocated to the HBE and the control group, in both the first and second period of study.
- 3. To assess therapeutic adherence and adverse event occurrence periodically by means of telephone call and photographic documentation of patient compliance with assigned intervention.

PATIENTS AND METHODS

General design: Randomized single-blind single-centre controlled clinical trial with a 2x2 cross-over design, in a sample of patients attending to the outpatient visit at the Gastroenterology, Digestive endoscopy and Liver Diseases Unit in Clínica Fundadores, Bogotá city. Participants who meet the inclusion and have no exclusion criteria will be randomized to raise the head of bed with standard 20 cm-height wooden blocks or to sleep without bed inclination during 2 periods of 6 weeks each, separated by a washout 2 week period. During the trial, every patient will receive standard pharmacological treatment with a proton pump inhibitor and/or sodium alginate, according to treating physician criteria, and the researchers in charge of statistical analysis and reporting results will be blinded for the non pharmacological intervention under study. Primary outcome is a significant symptom reduction according to RDQ validated questionnaire and secondary outcomes include quality of life impact according to SF-36 validated questionnaire, patient preference and adverse events of non pharmacological intervention.

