Cross-over: After allocation has been completed, patients in the intervention group will receive a pair of numbered wooden prisms with dimensions 20x18x18 cm along with written instructions about the correct use of the intervention. The patient must sleep with HBE during 6 weeks and both RDQ and SF-36 questionnaires will be applied again at the end of this first period while the participant is still sleeping with HBE. Afterwards, a washout 2 week period follows in which the participant sleeping with HBE will stop using it and will return the pair of wooden prisms to the researchers. After washout period has ended and both RDQ and SF-36 questionnaires have been applied again, patients allocated to the control group during the first period of the study will receive a random pair of prisms and will be instructed to use the prisms for sleeping with HBE during a second period of 6 weeks. Meanwhile, participants initially allocated to the HBE group will be followed as a control group in this second period of the study.

Blinding: Because HBE is not susceptible to double-blinding, patients allocated to the intervention group will always be aware of the group they belong to. However, the researcher in charge of statistical analysis of data and writing the results report will work with random-generated alphabetical group codes for masking the intervention in each one of the periods of the trial.

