Follow-up: After participant allocation, telephonic follow up will be made during both periods of the trial with a frequency that is dependent on the intervention group of the patient in that period. Participants in the HBE group will be called weekly for 2 weeks, and then will be called biweekly for a month, until each period of 6 weeks has ended. In contrast, patients in the control group will be called every three weeks along each period. With the purpose of verifying both HBE adherence and correct use of wooden prisms, every participant will be asked to send a photograph of the bed head legs during the follow-up telephone call. The photograph will be received by the researcher via e-mail or smartphone and will be encoded and saved in a hard disk. At the end of the first period, RDQ and SF-36 questionnaires will be applied and researchers will store the returned prisms during washout period. When washout period has ended, RDQ and SF-36 questionnaires will be applied again in order to be sure of the absence of any carry-over effect in the group initially allocated to HBE. Finally at week 14, RDQ, SF-36 and Patient Preference questionnaires will be administered to complete study ending outcome assessments.

In figure 5, a schematic representation of follow-up is shown.

[figure not shown]

Figure 5: Schematic representation of photographic and telephonic follow-up. W1-6: Weeks from 1st to 6th in each period.

Primary outcome:

1. Effectiveness: Change of ≥ 0,6 points between basal RDQ questionnaire and the same questionnaire administered after 6 weeks of HBE use.

Secondary outcomes:

- 1. Quality of life: Change of ≥ 10 percentage points between basal SF-36 questionnaire and the same questionnaire administered after 6 weeks of HBE use.
- **2. Patient preference:** Proportion of patients who preferred HBE, after finishing 14 weeks of the study.
- 3. Safety: Proportion of patients with any reported adverse event during HBE or without bed inclination.

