between periods will be transformed into a binomial variable and a McNemar marginal homogeneity test will be applied. McNemar mid-p was used if discordant pairs sum was smaller than 25²⁸. Differences with one-tail p<0,05 will be accepted as statistically significant. Exploratory subgroup analysis will search for differences stratified according to age group, sex, ethnic group, BMI, comorbidities, cups of coffee per day, pharmacological adherence, and length and severity of symptoms; among other 16 baseline variables. Subgroup interactions will be tested with Chi-square or Fisher exact test, and effect size was expressed as a univariate relative risk from a generalized linear model of binomial family. As part of internal quality control of the clinical trial, a pre-test was applied to prove the assumption of a negligible *carry-over* effect, according to expert guidelines²⁹. Analysis of variance (ANOVA) for crossover studies was used in search for significant sequence, period and treatment effects, assuming a negligible *carry-over* effect. In the modified intention to treat analysis, participants with protocol violations because of bad adherence to HBE, were included, but it was not possible to include patients who withdrew from the study because outcome information could not be gathered completely.

Methodology diagram: A schematic representation of the trial methodology is presented in figure 6.

[figure not shown]

Figure 6: Schematic representation of the trial methodology. RDQ: Reflux Disease Questionnaire; SF-36: Short Form 36 Questionnaire; HBE: Head of Bed Elevation; Standard treatment: Based on proton pump inhibitors and/or sodium alginate, according to treating physician criteria.

WORK TEAM

Work team of this clinical trial is formed by three authors. The respective roles during the design and conduction of the trial, and also the professional profiles of each researcher are described below.

Researchers:

- [name] (Principal Researcher study design, patient recruiting, telephonic follow-up, outcome assessment, statistical analysis, writing of final report)
 - General Practice Physician Universidad Nacional de Colombia
 - 3rd year Internal Medicine resident Universidad Nacional de Colombia
- [name](Researcher patient recruiting, intervention administration, clinical and telephonic follow-up, writing of final report)
 - General Practice Physician Universidad Nacional de Colombia

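### The RDQ and SF-36 outcomes count change from an undefined basal score to the end of HBE, with no no-HBE counterpart, so the response rate cannot be attributed to HBE

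*Combined protocol and SAP*

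**What the plan says.** Primary outcome: "Change of ≥ 0,6 points between basal RDQ questionnaire and the same questionnaire administered after 6 weeks of HBE use". Secondary outcomes, quality of life: "Change of ≥ 10 percentage points between basal SF-36 questionnaire and the same questionnaire administered after 6 weeks of HBE use". Neither entry says which questionnaire is basal, and neither defines the corresponding responder for six weeks without HBE.

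General design describes treatment "during 2 periods of 6 weeks each, separated by a washout 2 week period". Under Cross-over, after the washout, "patients allocated to the control group during the first period of the study will receive a random pair of prisms". RDQ and SF-36 are therefore scored at weeks 0, 6, 8 and 14. Under Follow-up the week-8 scores have one stated purpose: "RDQ and SF-36 questionnaires will be applied again in order to be sure of the absence of any carry-over effect". The last assessment is given as "Finally at week 14, RDQ, SF-36 and Patient Preference questionnaires will be administered".

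The Statistic analysis plan does not refer back to the basal score. For complementary processing of both outcomes, it says that the score difference "between periods will be transformed into a binomial variable and a McNemar marginal homogeneity test will be applied", without a cut-off. Figure 2, which underlies the McNemar sample size of 34, cross-tabulates two yes/no answers per patient: improved with HBE and improved without HBE.

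**The concern.** In a crossover trial the evidence lies in the contrast between a patient's two periods. The outcome as written is an uncontrolled before-after change under HBE. All patients also receive a proton pump inhibitor and/or alginate, and entry requires frequent symptoms, so scores may fall for reasons other than HBE (drug effect, time, regression to the mean). For patients who get HBE second, a week-0 anchor also takes in 6 control weeks and 2 washout weeks. For example, a patient scoring 3.3 at week 0 and 2.6 at weeks 6, 8 and 14 has a change of 0.7 and is an HBE responder, although nothing changed under HBE.

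The outcome section, the McNemar sentence and Figure 2 also describe three different variables: one change per patient from basal, one difference per patient between periods, and two yes/no answers per patient. The analyst would have to choose among them.

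**Working it through.** **1. The plan's own figure.** Figure 2 multiplies the two improvement rates as if independent: 0.588 × 0.714 = 0.420 and 0.412 × 0.286 = 0.118, giving 0.538 discordant and a ratio of about 3.57. With 34 × 0.538 = 18.3, taken as 18 discordant pairs, and rejection at 13 or more, the binomial tail is 0.0481 under the null and 0.8169 at p = 0.4202/0.5378 = 0.781. Both match Table 3. N=34 therefore rests on two yes/no answers per patient.

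**2. Time spanned.** HBE first: week 0 to week 6, all with HBE. HBE second: week 0 to week 14, with HBE only from week 8, so 6 + 2 = 8 weeks without it.

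**3. Response rate with no HBE effect, week-0 anchor.** The RDQ SD of 1.0 is from Sample size. The correlation ρ and a common non-HBE fall D, present from week 6 on, are assumptions; the documents give neither. The SD of a change is √(2(1−ρ)) = 1.0 at ρ = 0.5, and the rate is P(Z > 0.6 − D):

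- D = 0: P(Z > 0.6) = 27%
- D = 0.5: P(Z > 0.1) = 46%
- D = 1.0: P(Z > −0.4) = 66%

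The no-HBE period gives the same three rates. In simulations with 17 patients per sequence, one-sided McNemar mid-p on the week-0 responders rejected in fewer than 5% of null trials.

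**4. Power at N=34 under three definitions.** Simulation with an HBE effect of 0.6, no carry-over, 17 patients per sequence and unadjusted one-sided McNemar mid-p. Entries at ρ = 0.5 are for D = 0 / 0.5 / 1.0; the other rows give the range over D.

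| ρ | Week-0 anchor | Period-start anchor | Direct end-of-period difference |
|---|---|---|---|
| 0.3 | 54–62% | 40–49% | 82–83% |
| 0.5 | 73 / 74 / 64% | 60 / 58 / 47% | 92% at every D |
| 0.7 | 77–91% | 58–78% | 99% |

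The direct column can be checked by hand at ρ = 0.5. The difference has mean 0.6 and SD 1.0, so P(≥ 0.6) = 0.50 and P(≤ −0.6) = P(Z < −1.2) = 0.115. That makes 61.5% discordant, with a gap of 0.50 − 0.115 = 0.385. With the week-0 anchor at D = 0 the rates are 0.50 and 0.27, a gap of only 0.23.

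**5. Where the shortfall comes from.** With the week-0 anchor at ρ = 0.5, discordant pairs are 36% at D = 0, 37% at D = 0.5 and 29% at D = 1.0. The gap to the direct rule is already there at D = 0, with no pre-HBE improvement. It comes mainly from dichotomising change from a noisy baseline score.

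**6. Period effect.** With no HBE effect, an assumed 11/23 split of sequences and an assumed 0.5-point drift from week 6 to week 14, the unadjusted direct rule rejected in about 19% of trials and the week-0 rule in about 14%. Neither is safe without allowing for period.

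**The case against.** The strongest case on the other side is that little of this reaches the inference. *Basal* is undefined rather than wrongly defined. The timeline (Table 2) marks basal questionnaires in more columns than patient sampling, which could fit a baseline per period, although the extracted table is too broken to settle it. The McNemar test is complementary, and its score difference between periods reads naturally as a between-period contrast. The crossover ANOVA covers sequence, period and treatment. In the model above at ρ = 0.5, a paired t test on the end-of-period scores has 96% power (0.6 × √34 = 3.50 standard errors). All of this stands, and it limits the consequence.

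Three stronger readings are tempting and are not supported.

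- A reader might infer that the comparison is biased towards HBE. With balanced sequences the same anchor credits the no-HBE period equally, and type I error stays below 5%.
- A reader might infer that improvement before week 8 removes discordant pairs and so undermines N=34. The documents do not show that McNemar uses the basal anchor, and step 5 shows that such improvement is not the main cause of lower power.
- A reader might infer that a worsening of 0.6 counts as success because the change is unsigned. The executive summary and General design specify symptom reduction, and the hypotheses under Sample size are directional.

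Re-anchoring period 2 to week 8 is not the remedy: it had the lowest power at every setting in step 4.

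None of this repairs the stated outcome, which still has no comparator, or reconciles the three variables.

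**Conclusion.** The point holds for the outcome definition. As written, the RDQ and SF-36 response rates cannot be attributed to HBE on any reading of *basal*, because there is no no-HBE counterpart. On the week-0 reading, the HBE-second patients add 8 weeks of non-HBE change. The size is 27% to 66% apparent responders with no HBE effect, at ρ = 0.5 and assumed falls of 0 to 1.0 points.

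The direct end-of-period definition has about 82–99% power over ρ from 0.3 to 0.7, against 54–91% with a week-0 anchor and 40–78% with a period-start anchor. These figures assume SD 1.0, an effect of 0.6, balanced sequences and an unadjusted test. They are a reason to prefer the direct definition, not evidence that the planned McNemar test is underpowered. They concern RDQ; SF-36 was not simulated.

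**What to change.** Define effectiveness as the within-patient contrast of the two end-of-period scores:

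- RDQ, no-HBE minus HBE: at least 0.6 favours HBE, at most −0.6 favours no HBE, anything between is no difference.
- SF-36, HBE minus no-HBE: the same with +10 and −10.

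Use the two *favours* counts as the discordant pairs and report both. Even with no HBE effect, 27% would fall on each side at ρ = 0.5, so neither count should be read alone. Analyse them with account for period or sequence, for example with a Mainland-Gart or Prescott test, alongside the crossover ANOVA. Keep change from week 0 as description only, and say there that basal means week 0. Bring the outcome sections, the Statistic analysis plan and Figure 2 into line with this.

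The cost is wording, since every score is already collected. There is one real downside: the endpoint no longer matches the 58.8% and 28.6% improvement rates behind N=34. The stated McNemar power should therefore be restated for the new definition, or described as applying to the current one. The power of the period-adjusted test was not computed here and should be part of that restatement.

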The trial will be conducted during 8 months and will be divided into 4 successive stages.

- 1. Stage I: 2 months during which the first 4 specific objectives will be accomplished.
- 2. Stage II: 4 months for specific objectives 5 to 7.
- 3. Stage III: 1 month for specific objective 8 and results discussion.
- 4. Stage IV: 1 month for specific objectives 9 and 10.

In figure 1 and table 2, different stages with respective component activities are outlined.

[figure not shown]

Figure 1: Clinical trial stages

Patient recruitment: Because of a low recruitment rate, an active participant search system was finally implemented. This system was based on telephone calls, using a database with patient data from all upper gastrointestinal endoscopies performed in the Gastroenterology Unit at Clínica Fundadores in Bogotá city, between years 2014 to 2016. Patients were pre-selected based on endoscopically diagnosed erosive esophagitis of any grade, which is one of the clinical trial inclusion criteria. In order to minimize selection bias, 2 interviewers performed telephone calls in a consecutive chronologic order to all patients in the database without exception. In all cases, the same standardized telephone call format was used.

Sample size: Null hypothesis (H_0) and unidirectional alternative hypothesis (H_1) of the trial are represented below:

$$H_0$$
: RDQ_{HBE}= RDQ_{NoHBE} H_1 : RDQ_{HBE}< RDQ_{NoHBE} H_0 : SF-36_{HBE}= SF-36_{NoHBE} H_1 : SF-36_{HBE}> SF-36_{NoHBE}

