Sample size was estimated based on the hypothesis that HBE would produce a difference of at least 10% in RDQ and SF-36 scores. Effect size (Cohen d) was calculated as 0,49 keeping in mind an RDQ mean and standard deviation of 3,3±1,0 previously found in Spanish population with symptomatic GERD²⁴ and an SF-36 mean and standard deviation of 56,9±20,3 reported in Italian population in medical therapy with PPI²⁵. The minimally important difference selection was chosen based on the assumption that any difference smaller than 10% would have no clinical relevance. Based on this data, 14 patients per group would yield a power greater than 80% for detection of a minimally important difference as large as or larger than 0,6 points in RDQ questionnaire (range: 1 to 6) and 10 points in SF-36 questionnaire (range: 0 to 100), when using a paired t test as described in the statistical analyses plan section. Because of a complementary analysis of crossover data is planned with McNemar marginal homogeneity test, effect size was recalculated based on results of a previous trial²⁰, according to which, 58,8 % and 28,6% of placebo-treated patients in pre-omeprazole era, reported improvement of GERD symptoms with and without a HBE of 20 cm, respectively. Based on these data, and maintaining a statistical power of 80%, required sample size was adjusted to a total of 34 patients. In

figure 2, matrices for sample size calculation are shown, based on the cited trial and using internationally accepted statistical procedures²⁶. Likewise, in table 3 an output of sample size calculation is shown from G*Power 3.1.9.2 (Universität Düsseldorf, Düseldorf, Germany) software²⁷. Finally, calculated sample size was increased by 20% in order to avoid study power loss due to drop-outs or losses of follow-up. Thus, final sample size was 42 patients, 21 per group.

T test	Means: Difference between two dependent means	(matched pairs)
Analysis	A priori: Compute required sample size	
Input	Tails	One
	Effect size dz	0,4926108
	A err prob	0,05
	Power (1- β err prob)	0,8
Output	Noncentrality parameter δ	2,5596808
	Critical t	1,7056179
	Degrees of freedom	26
	Total sample size	27
	Actual power	0,8015888
McNemar	Proportions: Inequality, two dependent groups	
Analysis	A priori: Compute required sample size	
Input	Tails	One
	Odds ratio	3,571
	α	0,05
	1- β	0,8
	Prop discordant pairs	0,53782
Output	Lower critical N	13,0000000
	Upper critical N	13,0000000
	Total sample size	34
	Actual power	0,8169370

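### The primary outcome cuts RDQ change to a yes/no at 0.6 points although the hypotheses concern the score; the cut needs roughly 1.6 to 2.8 times the patients

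*Combined protocol and SAP*

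**What the plan says.** The Primary outcome section has one entry: "Change of ≥ 0,6 points between basal RDQ questionnaire and the same questionnaire administered after 6 weeks of HBE use". The quality-of-life outcome has the same form, with a cut at 10 points on SF-36.

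The Sample size section starts from the scores: "Null hypothesis (H_0) and unidirectional alternative hypothesis (H_1) of the trial are represented below", and the statements that follow compare RDQ and SF-36 under HBE and no HBE. It then sizes the trial on the score with a paired t test ("Effect size (Cohen d) was calculated as 0,49"; Table 3 gives 27 patients). A second calculation follows: "Because of a complementary analysis of crossover data is planned with McNemar marginal homogeneity test, effect size was recalculated". With rates of 58.8% and 28.6% taken from an earlier trial, and "maintaining a statistical power of 80%, required sample size was adjusted to a total of 34 patients". After the dropout allowance the total is 42.

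The Statistic analysis plan lists an unpaired t test or Mann-Whitney test for continuous variables, McNemar as complementary processing of a dichotomised score difference, and a cross-over ANOVA. The criterion is "Differences with one-tail p<0,05 will be accepted as statistically significant".

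**The concern.** The outcome labelled primary is a threshold, while the hypotheses, the first sizing and the cross-over ANOVA concern the score. Under the threshold, an improvement of 0.5 points and a worsening of 2 points count alike. Cutting a measured score this way costs power, which matters in a 42-patient trial that reports low recruitment. The number of patients was also raised from 27 to 34 for the binary analysis, using rates that are not rates of passing 0.6 RDQ points. If the yes/no result decides the conclusion, a real 0.6-point benefit could be missed that the score would show.

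**Working it through.** **Plan's own figures.**
- Paired t: the effect size 0.4926 is 10/20.3, the SF-36 ratio. Noncentrality is 0.4926 × √27 = 2.560, critical t is 1.706 and power is 0.8016, so N = 27 is reproduced.
- McNemar: with discordant cells 0.4202 and 0.1177 (odds ratio 3.571), N = 34 gives 0.8169 as in Table 3. Power is 0.810 with the mid-p version that the plan names for small discordant counts.

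**Inputs for the comparison.** From the Sample size section: target difference 0.6 points, "RDQ mean and standard deviation of 3,3±1,0", and 34 evaluable patients of 42. From the Statistic analysis plan: one-tailed 5% and mid-p McNemar. Assumed, because the documents do not give them: normal scores, a constant shift, a within-patient correlation r from 0 to 0.7, and a no-HBE responder rate of about 27% to 50%. The outcome text defines response only under HBE; the same cut is applied here to the no-HBE period.

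**Formulas.**
- Score: dz = 0.6/√(2(1−r)), with paired t power from the noncentral t distribution.
- Cut: bivariate normal changes, each cut at 0.6, give the two discordant probabilities, which go into mid-p McNemar power.

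The change can be modelled in two ways:
- Model A: every score has SD 1.0, any two scores correlate at r, and both periods share one baseline. The change SD is √(2(1−r)), and the two changes correlate at (1−r)/(2(1−r)) = 0.5 whatever r is.
- Model B: each change has SD 1.0 and the two changes correlate at r.

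| r | dz | Score: N for 80% | Score: power at 34 | A, cut: N (ratio) | A, cut: power at 34 | B, cut: N (ratio) | B, cut: power at 34 |
|---|---|---|---|---|---|---|---|
| 0 | 0.424 | 36 | 78% | 76–79 (2.11–2.19) | 47–49% | 56–58 (1.56–1.61) | 60–61% |
| 0.3 | 0.507 | 26 | 89% | 54–55 (2.08–2.12) | 60–61% | 46–48 (1.77–1.85) | 67–69% |
| 0.5 | 0.600 | 19 | 96% | 40 (2.11) | 73–74% | 39–40 (2.05–2.11) | 73–75% |
| 0.7 | 0.775 | 12 | >99% | 26–27 (2.17–2.25) | 89–91% | 32–34 (2.67–2.83) | 81–83% |

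At r = 0.5 in Model A with a 28.6% no-HBE rate, the discordant cells are 0.297 and 0.070. With all 42 patients evaluable, the cut then has 82% power and the score more than 98%.

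**What the binary target implies.** With a change SD of 1.0, moving 28.6% to 58.8% needs a shift of Φ⁻¹(0.588) − Φ⁻¹(0.286) = 0.222 + 0.565 = 0.79 points. A shift of 0.6 moves 28.6% only to Φ(−0.565 + 0.6) = 51%.

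**The case against.** The strongest reply is that the score is already analysed. The hypotheses are about scores, the plan calls McNemar complementary, and a cross-over ANOVA is listed. On that reading 0.6 is a relevance margin, not a decision rule. Much of this stands. A reader might infer that the trial throws away about half its information; the documents do not support that. What remains is that the only outcome named primary is the threshold, and nothing says that the score analysis takes precedence.

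A second reply is that the plan paid for the cut by raising 27 to 34, a ratio of 34/27 = 1.26, and has 81–82% power at its binary target. That is correct on its own terms, so the binary analysis is not underpowered at 58.8% versus 28.6%. But those rates are reported improvement in an earlier trial and correspond to a larger shift than 0.6 points under the assumption shown.

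Third, the size depends on the model. A reader might infer a constant two-fold cost or a loss of more than 20 points in every case. The near-constant ratio in Model A is built in, because a shared baseline with equal correlations fixes the correlation of the changes at 0.5. The loss is only 9–11 points at r = 0.7 in Model A, and 17–18 points at r = 0 in Model B.

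Finally, RDQ is bounded and the plan expects some non-normal data, so the score's advantage may be smaller than modelled. The plan's McNemar text also dichotomises the difference between periods, while the outcome text uses change from baseline. The variable to be analysed is therefore itself unsettled.

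**Conclusion.** The point holds as a mismatch with a material but uncertain cost. At a 0.6-point difference, SD 1.0 and one-tailed 5%, the cut needs roughly 1.6 to 2.8 times the patients, and about 2.1 times (40 versus 19) at a correlation of 0.5. The power loss at 34 evaluable patients runs from about 9 to 31 points over correlations of 0 to 0.7 and both models. At 0.5 it is about 23 points (73% versus 96%), and the cut recovers to about 82% only if there are no losses from the 42. All of this rests on assumed correlations and normal scores. The direction is the same in every scenario tried.

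Using Table 3's effect size of 0.49 in place of 0.60 does not change the picture: at a correlation of 0.5 between the changes, it gives 27 versus 56–58 patients. If each period were measured from its own start score, with all scores equally correlated, the multiple would be higher still (57–58 versus 19 at r = 0.5). I do not rely on that, because the outcome text refers only to the basal questionnaire.

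**What to change.** In the Primary outcome section, define the primary outcome as the within-patient difference in RDQ score between the end of the HBE period and the end of the no-HBE period (weeks 6 and 14, in either order). In the Statistic analysis plan, name the cross-over ANOVA as its analysis, in place of the unpaired test, and report the mean difference with a 95% confidence interval read against 0.6. Keep the 0.6-point responder with McNemar as a supportive outcome, and state which dichotomised variable it uses. Do the same for SF-36 and 10 points.

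End-of-period scores are preferable to change from each period's own start. With equal correlations the difference of two changes has variance 4(1−r), against 2(1−r) for the difference of two end scores.

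The cost is wording: no extra visit, questionnaire or patient. The small downside is that the headline becomes a mean difference; the responder proportion is still reported. Parts of the Statistic analysis plan are in the past tense, so the change should be dated relative to the unmasking of the group codes.

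### Patient preference counts only patients who finish week 14, so those who leave because of the raised bed are not counted and the proportion preferring HBE can be overstated

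*Combined protocol and SAP*

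**What the plan says.** Under Secondary outcomes, item 2 is the "Proportion of patients who preferred HBE, after finishing 14 weeks of the study". The Follow-up section fixes the only time at which it is measured: "Finally at week 14, RDQ, SF-36 and Patient Preference questionnaires will be administered to complete study ending outcome assessments". Week 14 is the end of the second period (6 + 2 + 6 weeks). RDQ and SF-36 are also applied at the end of the first period and after washout; the preference questionnaire is not.

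The Statistic analysis plan says of the modified intention-to-treat analysis that "it was not possible to include patients who withdrew from the study because outcome information could not be gathered completely". The same sentence keeps another group in: "participants with protocol violations because of bad adherence to HBE, were included".

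The Sample size section expects losses. The requirement is given as "required sample size was adjusted to a total of 34 patients", then "increased by 20% in order to avoid study power loss due to drop-outs or losses of follow-up", so that the "final sample size was 42 patients, 21 per group".

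The documents describe no preference question at early exit, no rule for counting withdrawals in this outcome and no sensitivity analysis for it. They give no expected preference rate, no specific test for it, and neither a count of withdrawals nor their reasons.

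**The concern.** For a symptom score, leaving the study may or may not be related to the outcome. For preference the link can be direct: a patient who leaves because the raised bed was unacceptable has in effect answered the question, and the outcome definition discards that answer. HBE is used every night for six weeks and patients know when they are using it, so exits for this reason are plausible.

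At stake is how the preference result reads. If exits because of HBE are the main kind, then the less tolerable HBE is, the more unfavourable answers disappear from the denominator. Repairing the analysis set for RDQ and SF-36 would not solve this, because the completion condition and the single time point belong to the preference outcome itself. The primary RDQ result does not depend on the preference questionnaire.

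**Working it through.** **Inputs from the documents.** Randomised N = 42; required evaluable number 34; allowance 20% (Sample size). Preference is taken once, at week 14 (Follow-up). Withdrawals are left out (Statistic analysis plan).

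**Reproducing the plan's 34 and 42.** Table 3 gives a discordant proportion of 0.53782 and an odds ratio of 3.571. Discordant pairs: 34 × 0.53782 = 18.3, taken as 18. With a critical count of 13, the one-sided binomial tail at 0.5 is 0.0481, and at 3.571/4.571 = 0.781 it is 0.8169. Both match Table 3. For the allowance, 34 × 1.2 = 40.8 and 34/0.8 = 42.5; the stated 42 lies between them and splits evenly into 21 + 21. The plan thus leaves room for 42 − 34 = 8 withdrawals. It has no figure for preference to reproduce.

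**Formulas.** Let w patients withdraw, n = N − w finish, and x finishers prefer HBE. Suppose k of the w would have preferred HBE.

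- Reported figure: x/n
- Figure for all randomised: (x + k)/N, ranging from x/N (k = 0) to (x + w)/N (k = w)
- Largest overstatement: x/n − x/N = (x/n) × (w/N)
- Break-even: k = w × x/n

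**Results.** The values of w and x are assumptions, chosen so that about 70% of finishers prefer HBE.

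| w | Finishers only | All withdrawals against HBE | All withdrawals for HBE | Largest overstatement |
|---|---|---|---|---|
| 8 | 24/34 = 70.6% | 24/42 = 57.1% | 32/42 = 76.2% | 13.4 points |
| 4 | 27/38 = 71.1% | 27/42 = 64.3% | 31/42 = 73.8% | 6.8 points |
| 2 | 28/40 = 70.0% | 28/42 = 66.7% | 30/42 = 71.4% | 3.3 points |
| 0 | 29/42 = 69.0% | 29/42 = 69.0% | 29/42 = 69.0% | 0 |

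At w = 8 the largest overstatement is 8/42 = 19% of whatever rate is reported. At 27/34 = 79.4% that is 15.1 points (27/42 = 64.3%).

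**Direction.** For 24/34 and w = 8, break-even is 8 × 24/34 = 5.6. If 5 or fewer of the 8 would have preferred HBE, the finishers' figure is too high (29/42 = 69.0% at k = 5). If 6 or more would have, it is too low (30/42 = 71.4% at k = 6).

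**Exits before HBE.** The bounds above treat every withdrawal as having used HBE. If, say, 4 of the 8 left before using it in the trial, the HBE users number 34 + 4 = 38, and the bounds narrow to 24/38 = 63.2% and 28/38 = 73.7%.

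**The case against.** Four arguments deserve weight.

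- **Stopping HBE is not leaving the study.** Patients with poor adherence are kept in the analysis. Someone who gives up the blocks but stays can answer against HBE at week 14. This stands, and it limits the problem to those who leave the study altogether.
- **Loss can run the other way.** In this crossover, HBE-first patients return the blocks and are then followed as controls. One who liked HBE and leaves during washout or the control period is a lost favourable answer. Control-first patients who leave before their HBE period have no trial experience of HBE to report. A reader might infer that the selection works in one direction only; the design does not support that.
- **Intolerance can surface elsewhere.** Telephone calls and photographs follow adherence and adverse events, and the safety outcome counts any adverse event reported during HBE. This stands in part. Simple dislike or a partner's objection need not be recorded as an adverse event, and a safety count does not correct the preference denominator.
- **Asking after both conditions is natural in a crossover.** It is a reasonable definition, and for that reason the finishers' figure should stay. One could reply that patients who leave during HBE already know a flat bed from before the trial, but the eligibility criteria neither exclude nor record earlier head elevation, so that cannot be assumed.

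**Conclusion.** The point holds as a risk of bias in a secondary outcome. Preference is measured among completers only, by its definition, its schedule and the withdrawal rule, and patients who leave because of HBE are not counted. The proportion preferring HBE can therefore be overstated. At the planned 8 withdrawals the extreme bound is 19% of the reported rate, for example 70.6% against 57.1%. With 2 withdrawals it is about 3 points, and with none it is zero.

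These sizes rest on an assumed finishers' rate, an assumed number of withdrawals and the extreme case that every one of them is against HBE. The 20% allowance covers losses of any cause, so that case is a limit and not an expectation.

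A reader might infer that the figure is inflated as a matter of fact. The documents do not support this, since they report neither how many left nor why, and the sign reverses if those who left favoured HBE more often than finishers. A reader might also infer that a significant majority for HBE would be lost. The plan sets no test against 50% and no threshold for preference, so that reading has no basis in it.

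**What to change.** 1. At early exit, put the same Patient Preference question to every patient who has used HBE in the trial, and record the reason for leaving.
2. Keep the finishers-only proportion and state its denominator. Beside it, report the proportion among all randomised patients who used HBE, including the exit answers.
3. For HBE users who left and could not be asked, add a symmetric sensitivity analysis. Count withdrawals attributed to HBE as not preferring it and withdrawals attributed to the flat bed as preferring it, and give best and worst case bounds for the rest.
4. Report the number of withdrawals by sequence, period and reason, so that readers can judge the direction themselves.

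The cost is one question and one reason field at exit, plus a second line in the results table. Some patients will not be reachable when they leave; the documents describe no exit contact, so one would have to be added. The resulting figure may be less favourable to HBE. The sentence on withdrawals is written in the past tense; if follow-up has already ended, the exit answers may not be recoverable, but the stated denominators, any reasons on file and the bounds can still be reported.
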